#### **15.2.4 Reporting of Outcomes**

All conclusions should be based on all eligible patients. Sub analyses may then be performed on the basis of a subset of patients, excluding those for whom major protocol deviations have been identified (e.g., early death due to other reasons, early discontinuation of treatment, major protocol violations, etc.). However, these sub analyses may not serve as the basis for drawing conclusions concerning treatment efficacy, and the reasons for excluding patients from the analysis should be clearly reported. The 95% confidence intervals should also be provided.

### **15.3. Study Design/Endpoints**

#### **15.2.5 Primary Endpoint**

The primary hypothesis of this study is that combination hypomethylation induction followed by PD-1 blockade maintenance will result in increased efficacy compared to standard of care chemotherapy. This will be evaluated by comparing time to disease recurrence or death in this study with historical controls. This is based on recent studies evaluating therapy options after failure of first-line therapy in metastatic pancreatic cancer. The recently completed cooperative group study (SWOG S1115) was designed to evaluate an experimental therapy compared to standard chemotherapy with a null hypothesis of median PFS of 2 months. The study was a negative study and as reported in December 2016 both arms resulted in PFS of around 2 months in this setting.

The **primary endpoint** is progression-free survival defined as the time from first treatment with the study drug to the earliest of either disease progression or death from any cause. Patients who are alive and progression free at the time of analysis will be censored at the time of their last follow-up. With 31 eligible subjects enrolling over 18 months with an additional 6 months of follow-up, we will have 80% power to detect a median PFS of 2 months in historical controls versus 4 months with one-sided alpha of 0.05.

The Kaplan-Meir method will be used to evaluate all time to event endpoints. Median progression-free survival will be reported with 95% confidence intervals.

#### **15.2.6 Secondary Endpoints**

The secondary hypothesis of this study is that combination therapy will lead to improvements in overall response rate (ORR), duration of response (DOR), disease control rate (DCR), and overall survival (OS). These will all be reported with percentages and 95% confidence intervals. The Kaplan-Meir method will be used to evaluate all time to event endpoints.

##### **15.2.6.1 Definition of secondary endpoints:**

###### **▪ Objective Response Rate**

- ORR is defined as the proportion of the subjects in the analysis population who have a CR or PR. Responses are based on assessments per RECIST 1.1 as described in Section 13.4.

- **Duration of Response**
  - For subjects who demonstrate CR or PR, based on assessments per RECIST 1.1, DOR is defined as the time from first documented evidence of CR or PR until disease progression or death due to any cause, whichever occurs first.
- **Disease Control Rate**
  - DCR is defined as the percentage of subjects who have achieved CR, PR, or SD based on assessments per RECIST 1.1.
- **Overall Survival (OS)**
  - OS is defined as the time from first dose of study medication to death due to any cause.

#### **15.2.7 Exploratory and Ancillary Studies**

See [Section 13.6.3](#) for description of correlative studies. All subjects will be required to agree to an on treatment biopsy after 8 weeks of therapy. Given the patient population and the likelihood that some subjects will have disease or clinical progression precluding biopsies we estimate that we will obtain on-treatment biopsy samples from a minimum of 20 subjects.

- 15.2.7.1 Global DNA Methylation will be assessed in all subjects at baseline and every 2 weeks for the first 8 weeks of study. We will estimate the disease control rates (DCR) and time to event endpoints (median PFS and median OS) for subjects who have methylation below the median compared to above the median at baseline. We will also estimate these outcomes for those who achieve low methylation (<10% methylation) compared to normal methylation ( $\geq 10\%$  methylation) after 8 weeks of therapy. We will also estimate these outcomes for those who achieve a change in methylation greater than the median compared to higher than the median at 8 weeks (compared to baseline).
- 15.2.7.2 Fisher's exact test will be performed to compare the disease control rate for the two groups. Kaplan-Meier estimates of the survival distribution for the two groups will be calculated, and the two groups will be compared using a log-rank test. Change in methylation in tumor tissue will be evaluated in 20 patients who undergo baseline and week eight biopsies and will be compared using the paired t-test or the Wilcoxon signed-rank test depending on the data distribution. With 20 patients, we will have 80% power to detect a change of 0.66 standard deviations given an alpha of 0.05.
- 15.2.7.3 Change in methylation in tumor tissue will be evaluated in subjects who undergo baseline and week 8 biopsies. We will describe changes in specific gene methylation patterns as described in [Section 13.6.3](#).
- 15.2.7.4 Immune phenotyping will be measured on the subjects who undergo an on-treatment tumor biopsy. We will provide descriptive tables of IHC expression of CD8/CD3 T cell ratio, CD86/CD68 macrophage ratio, PD1 expression. Samples will be compared between pre and post combination specimens in treated subjects using the paired t-test.

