### **13.6.1 Efficacy Endpoints**

#### **13.6.1.1 Primary Efficacy Endpoint**

- Progression-Free Survival
  - PFS is defined as the time from the first day of trial treatment to the first documented disease progression per RECIST 1.1 or death due to any cause, whichever occurs first.

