### **13.6.3 Correlative Endpoints**

#### **13.6.3.1 Global DNA Methylation**

DNA methylation, using LINE-1 assay, will be determined and expressed as continuous variables with mean, median, and standard deviation calculations reported. Average changes in global DNA methylation will be assessed at baseline and every two weeks for the first eight weeks of the study. Disease control rates (DCR) and time to event endpoints (PFS and OS) will

be estimated for patients who have methylation below the median compared to above the median at baseline. We will also estimate these outcomes for those who achieve low methylation (<10% methylation) compared to normal methylation ( $\geq 10\%$  methylation) after eight weeks of therapy. We will also estimate these outcomes for those who achieve a change in methylation greater than the median compared to lower than the median at eight weeks compared to baseline.

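### For the two groupings by week-8 methylation, median PFS and OS counted from first dose include time a subject had to survive to be grouped; a fixed landmark removes it

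*Combined protocol and SAP*

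**What the plan says.** Section 15.2.7.1 lists three methylation groupings, each with disease control rate, median PFS and median OS. The first splits at the baseline median. The second is defined at week 8: "We will also estimate these outcomes for those who achieve low methylation (<10% methylation) compared to normal methylation" (10% or more). The third, also at week 8, uses the change from baseline: "We will also estimate these outcomes for those who achieve a change in methylation greater than the median compared to higher than the median". The closing words of that sentence are a slip; section 13.6.3.1 contrasts greater with lower. Section 13.6.3.1 dates the 10% split in the same way, "after eight weeks of therapy".

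Section 15.2.7.2 gives the method: "Kaplan-Meier estimates of the survival distribution for the two groups will be calculated, and the two groups will be compared using a log-rank test".

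The clock starts at first treatment. For PFS, section 13.6.1.1 says "PFS is defined as the time from the first day of trial treatment to the first documented disease progression per RECIST 1.1" or death, and section 15.2.5 has "time from first treatment with the study drug to the earliest of either disease progression or death from any cause". For survival, section 15.2.6.1 says "OS is defined as the time from first dose of study medication to death due to any cause".

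No section specifies a landmark, delayed entry or a time-dependent covariate for the week-8 groupings. None says what happens to subjects who die, progress or leave before the week-8 value exists. Section 15.2.7 itself expects progression to prevent some week-8 biopsies and counts on at least 20.

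**The concern.** A subject can be placed in a week-8 group only by reaching the sample. If the clock starts at first dose, the time before the sample is credited to the group although nobody in it could have died during that time. This is guaranteed-time (immortal-time) bias. It raises the group medians above what the same patients would show in an unselected cohort.

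For PFS there is a second difficulty. An event that occurs before the sample precedes the grouping that is supposed to explain it, so such events say nothing about what week-8 methylation predicts.

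What is at stake is the interpretation of the biomarker results. Section 1.1 wants these analyses to help identify predictors of response and survival.

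**Working it through.** **The plan's own figures.** The plan gives no number for the week-8 medians or for the log-rank comparison. The one methylation power figure in 15.2.7.2 (20 pairs, 0.66 SD, alpha 0.05, 80%) reproduces: the noncentral t gives 79.9% two-sided. It does not bear on the time origin.

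**Inputs.**
- Median PFS of 2 and 4 months, 31 subjects, 18 months of accrual and 6 of follow-up (15.2.5).
- At least 20 on-treatment biopsies (15.2.7).
- Week 8 = 56/30.4375 = 1.84 months; week 6 = 42/30.4375 = 1.38 months.
- Assumption, not in the documents: exponential PFS and OS. The documents give no OS median, so a range is used.

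**1. Share event-free at week 8**, S = 0.5^(1.84/m):
- m = 2: 0.5^0.92 = 0.529, or 16.4 of 31.
- m = 4: 0.5^0.46 = 0.727, or 22.5 of 31.

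**2. PFS, upper bound.** If nobody with an event before week 8 is grouped, the exponential has no memory and the day-1 median is 1.84 + m: 3.84 months (m = 2) or 5.84 (m = 4). At week 6 it is 3.38 or 5.38.

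**3. PFS, partial selection.** Suppose n of 31 are sampled and those missing are all early failures. The median then solves 0.5^(t/m) = n/62, so t = m × [1 + log2(31/n)], for n between 31 × S and 31.

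| Early failures not sampled | n, m = 2 | Median, m = 2 | n, m = 4 | Median, m = 4 |
|---|---|---|---|---|
| 0% | 31.0 | 2.00 | 31.0 | 4.00 |
| 25% | 27.3 | 2.36 | 28.9 | 4.41 |
| 50% | 23.7 | 2.78 | 26.8 | 4.85 |
| 75% | 20.0 | 3.26 | 24.7 | 5.32 |
| 100% | 16.4 | 3.84 | 22.5 | 5.84 |

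The plan's minimum of 20 corresponds to 2 × [1 + log2(1.55)] = 3.26 months at m = 2. At m = 4 it does not narrow the range, because 22.5 are expected event-free anyway. The minimum refers to biopsies, so it applies only if tissue supplies the week-8 value.

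**4. OS.** A subject must be alive to be sampled, so the guaranteed time is strict. For assumed OS medians of 4, 6, 8 and 10 months, grouped subjects show 5.84, 7.84, 9.84 and 11.84 from day 1. With a week-6 sample the shift is 1.38 months.

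**5. Log-rank test.** The statistic uses only the order of events. If both groups consist of subjects event-free at week 8, subtracting 1.84 months from everyone changes nothing. Simulation (20,000 runs, 31 subjects, no true difference, nominal two-sided 5%) confirms this:

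| Analysis | Type I error, m = 2 | Type I error, m = 4 |
|---|---|---|
| Both groups measured, from day 1 | 6.7% | 5.9% |
| Both groups measured, from landmark | 6.7% | 5.9% |
| Unmeasured early failures put with the non-achievers | 48% | 28% |

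**6. With a week-8 landmark.** The residual median is 2.0 or 4.0 months in theory. Simulated, it is 2.09 and 4.14, against 3.93 and 5.98 from day 1 in the same subjects.

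**The case against.** The strongest reply is that the PFS inflation may be modest. The first on-study scan and the biopsy both fall at week 8 with a 7-day window either side (12.1, footnotes k and m), so little radiographic progression can be documented much earlier. Sections 5.1 and 13.5 allow treatment beyond first progression. A subject whose week-8 scan shows progression can therefore still be sampled and enter with a PFS of about 1.84 months. This stands. The figures 3.84 and 5.84 are upper bounds, and more complete sampling moves the medians towards 2.0 and 4.0. It does not help OS.

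Three stronger readings are tempting, and the documents do not support them:

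- **That the log-rank test is invalid.** A reader might infer this because it is the method named. Between two groups that both need a week-8 value, the day-1 origin leaves its error rate unchanged. The large error arises only if unmeasured subjects are assigned to a group, which the text neither plans nor rules out. Section 15.2.7.2 also does not say which of the groupings its two groups come from, and the baseline split is unaffected.
- **That an ineffective treatment would appear to reach the 4-month target.** The comparison of 2 with 4 months belongs to the primary analysis of all treated subjects (15.2.3, 15.2.5, 15.7). Section 15.2.4 rests conclusions on all eligible patients and bars sub-analyses that exclude, for example, early deaths from supporting efficacy claims. No section compares methylation-group medians with 2 or 4 months.
- **That progression changes the methylation value.** The documents give no evidence for this. They show only that some PFS events may come before the measurement.

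**Conclusion.** The point holds for the two week-8 groupings and for their reported medians. Followed as written, the plan adds about 1.84 months of guaranteed time to OS (1.38 at week 6). To median PFS it adds between nothing and 1.84 months, depending on how many early progressors go unsampled. With 20 of 31 sampled and a true median of 2 months, the addition is about 1.26 months (3.26 − 2.00).

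The PFS figures rest on exponential times and on the missing subjects being early failures; with scans every 8 weeks, recorded progressions will cluster at the scan dates. The between-group test is sound only if unmeasured subjects stay out of it, and the plan should say so. This is an inexpensive improvement to an exploratory analysis. It leaves the primary result and the baseline-methylation groups untouched.

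**What to change.** First reconcile the sampling schedule. Section 12.1 (footnote n) and section 12.1.6.6 take blood at baseline and weeks 3, 5 and 6. Sections 13.6.3.1 and 15.2.7.1 assess global methylation every two weeks to week 8. Until this is settled, it is unclear whether the week-8 value comes from blood or tissue, or exists for all subjects.

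Then add to 15.2.7, for the two post-baseline groupings only:
- One fixed landmark for everyone, at the end of the window of the visit that supplies the grouping value. Using each subject's own sampling date would let the order of scan and biopsy within their windows decide who is excluded.
- OS and PFS start at the landmark. Include only subjects with a methylation value who are alive at it (OS), or alive and progression-free at it (PFS).
- Subjects without a value are not assigned to a group.
- Report the number excluded and label the medians as counted from the landmark.

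Baseline-methylation groups stay counted from day 1.

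The drafting cost is a few lines, but the loss of subjects is not trivial. At an 8-week landmark the PFS comparison may lose up to 1 − 0.529 = 47% of 31 subjects at a true median of 2 months, leaving about 16, or roughly 8 per group in a median split. At a median of 4 months it may lose 27%. If the 7-day biopsy window puts the landmark at 9 weeks (63/30.4375 = 2.07 months), these become 1 − 0.5^(2.07/2) = 51% and 1 − 0.5^(2.07/4) = 30%. Part of that loss has already occurred wherever early progressors were never sampled. The OS comparison loses few or none of those sampled.

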#### **15.4. Size/Accrual Rate**

A total of 31 subjects will be enrolled over 18 months with plan to screen 4-5 subjects in our

multi-disciplinary pancreas clinic each month with enrollment of 2-3 patients per month. If the original 6 patient DLT cohort requires a dose reduction then up to a maximum of 37 subjects will be enrolled with 31 additional enrolled at the final dose level.

### **15.5. Stratification Factors**

No stratification is planned.

### **15.6. Statistical Methods for Safety Analysis**

Safety and tolerability will be assessed by clinical review of all relevant parameters including adverse experiences (AEs), laboratory tests, and vital signs. Count and percentage AE will be provided. Confidence interval rate of AE of clinical interest will be estimated using Exact method based on binomial distribution.

### **15.7. Analysis Populations**

All subjects who received at least one dose of study treatment will be included in the primary and secondary efficacy and safety analysis as detailed in [Section 15.2](#).

## **16. PROTECTION OF HUMAN SUBJECTS**

This study is to be conducted in accordance with applicable government regulations and Institutional research policies and procedures.

This protocol and any amendments will be submitted to a properly constituted Institutional Review Board (IRB), in agreement with local legal prescriptions, for formal approval of the study conduct. The decision of the IRB concerning the conduct of the study will be made in writing to the investigator and a copy of this decision will be obtained before commencement of this study.

All subjects for this study will be provided a consent form describing this study and providing sufficient information for subjects to make an informed decision about their participation in this study. This consent form will be submitted with the protocol for review and approval by the IRB for the study. The formal consent of a subject, using the IRB-approved consent form, must be obtained before that subject is submitted to any study procedure. This consent form must be signed by the subject or legally acceptable surrogate, as outlined in the IRB approved protocol, and the investigator-designated research professional obtaining the consent.

## **17. STUDY FINANCES**

### **17.1. Conflict of Interest**

N/A

### **17.2 Subject Stipends or Payments**

N/A

## 18. PUBLICATION PLAN

Neither the complete nor any part of the results of the study carried out under this protocol, nor any of the information provided by the sponsor for the purposes of performing the study, will be published or passed on to any third party without the consent of the study sponsor. Any investigator involved with this study is obligated to provide the sponsor with complete test results and all data derived from the study.

## 20. APPENDICES

### 20.1. Appendix 1- ECOG Performance Status

Grade	Description
0	Normal activity. Fully active, able to carry on all pre-disease performance without restriction.
1	Symptoms, but ambulatory. Restricted in physically strenuous activity, but ambulatory and able to carry out work of a light or sedentary nature (e.g., light housework, office work).
2	In bed <50% of the time. Ambulatory and capable of all self-care, but unable to carry out any work activities. Up and about more than 50% of waking hours.
3	In bed >50% of the time. Capable of only limited self-care, confined to bed or chair more than 50% of waking hours.
4	100% bedridden. Completely disabled. Cannot carry on any self-care. Totally confined to bed or chair.
5	Dead.

\* As published in Am. J. Clin. Oncol.: *Oken, M.M., Creech, R.H., Tormey, D.C., Horton, J., Davis, T.E., McFadden, E.T., Carbone, P.P.: Toxicity And Response Criteria Of The Eastern Cooperative Oncology Group. Am J Clin Oncol 5:649-655, 1982.* The Eastern Cooperative Oncology Group, Robert Comis M.D., Group Chair.

### 20.2. Appendix 2- Common Terminology Criteria for Adverse Events V4.0 (CTCAE)

The descriptions and grading scales found in the revised NCI Common Terminology Criteria for Adverse Events (CTCAE) version 4.0 will be utilized for adverse event reporting.

<http://www.oncology.tv/SymptomManagement/NationalCancerInstituteUpdatesCTCAEtoV403.aspx>

### 20.3. Appendix 3- Response Evaluation Criteria in Solid Tumors (RECIST) 1.1

Criteria for Evaluating Response in Solid Tumors RECIST version 1.1 will be used in this study for assessment of tumor response. While either CT or MRI may be utilized, as per RECIST 1.1, CT is the preferred imaging technique in this study.

In addition, volumetric analysis will be explored for response assessment.
